#### 4.2.2 Randomized Treatment Period

Table 6 shows all procedures to be conducted during the treatment period.

**Table 6 Schedule of Treatment Period Study Procedures**

Study Period	Treatment Period							
Visit Number	V3	V4	V5	V6	V7	V8	V9	Early D/c Visit
Procedure / Study Day	Day 1	Day 29 (± 5 days)	Day 57 (± 5 days)	Day 85 (± 5 days)	Day 113 (± 5 days)	Day 141 (± 5 days)	Day 169 (± 5 days)	
Verify eligibility criteria	X							
Randomization	X							
Safety assessments:								
Physical examination (abbreviated) with weight a	X	X	X	X	X	X	X	X
Vital signs b	X	X	X	X	X	X	X	X
Transthoracic echocardiogram							X c	X
Assessment of AEs/SAEs	X	X	X	X	X	X	X	X
Concomitant medications	X	X	X	X	X	X	X	X
Blood collection for:								
Serum chemistry	X	X		X		X	X	X
CCI [REDACTED]	X	X		X			X	X
CCI [REDACTED]							X	X

**Table 6 Schedule of Treatment Period Study Procedures**

Study Period	Treatment Period								
	Visit Number	V3	V4	V5	V6	V7	V8	V9	Early D/c Visit
Procedure / Study Day	Day 1	Day 29 (± 5 days)	Day 57 (± 5 days)	Day 85 (± 5 days)	Day 113 (± 5 days)	Day 141 (± 5 days)	Day 169 (± 5 days)		
Complete blood count with differential, prothrombin time, and PTT	X				X			X	X
PK (MEDI3506) d		X			X			X	X
PK (dapagliflozin) e						X	X		
ADA (MEDI3506) f	X	X			X			X	X
CCI									
CCI									
Blood for future use f,g	X	X					X		X
Genetic research sample g,h	X								
Urine collection for:									
Urinalysis f	X								
Pregnancy test (females of childbearing potential) f	X	X	X	X	X	X	X	X	X
UACR i	X	X	X	X	X	X	X	X	X
CCI									
Urine for future use f,g	X	X			X		X		X
Procedure:									
Site to remind patients to collect first morning void midstream urine samples 3 days before the next visit		X	X	X	X	X	X	X	X
IP administration (MEDI3506/placebo) j	X	X	X	X	X	X			
IP administration (dapagliflozin) k				Day 85 to Day 168 QD					

ADA = anti-drug antibody(ies); AE(s) = adverse event(s); CCI  
D/c = discontinuation; CCI  
CCI ; IP = investigational product; PK = pharmacokinetics; PTT = partial thromboplastin time; QD = once daily; SAE(s) = serious adverse event(s); CCI ; UACR = urine albumin:creatinine ratio V= Visit.

NOTE: Investigator should ensure that all subjects are contacted by phone 1 day prior to every visit for assessing COVID-19 symptoms and signs and are asked to follow up suspected reports according to local guidelines. Any subject with symptoms consistent with COVID-19 should be tested on an ad hoc basis.

**Table 6 Schedule of Treatment Period Study Procedures**

Study Period	Treatment Period							Early D/c Visit
Visit Number	V3	V4	V5	V6	V7	V8	V9	
Procedure / Study Day	Day 1	Day 29 (± 5 days)	Day 57 (± 5 days)	Day 85 (± 5 days)	Day 113 (± 5 days)	Day 141 (± 5 days)	Day 169 (± 5 days)	

- a Including focused cardiac exam (Section 4.3.2.2).
- b For the first 2 doses of MEDI3506 or placebo, patients are to remain at the site for  $\geq 2$  hours or until stable, whichever is later. In addition, vital signs will be taken before and immediately after administration of MEDI3506 or placebo, and at 30 minutes ( $\pm 5$  minutes) as well as 120 minutes ( $\pm 10$  minutes) thereafter or until stable, whichever is later. Following the observation period, subject discharge will be at the discretion of the investigator. For all other dosing visits, vital signs will be collected 30 minutes ( $\pm 5$  minutes) after administration of MEDI3506 or placebo or when stable.
- c May be performed independently of other Visit 9 procedures within the visit window.
- d PK samples on MEDI3506/placebo dosing days will be collected pre-dose of MEDI3506/placebo administration.
- e Dapagliflozin PK samples will be collected at the following time points relative to dapagliflozin administration: Day 141 (predose and 2 h postdose) and Day 169 on study visit. Patients will be reminded to take dapagliflozin on site visits during dapagliflozin administration time (Day 85 to Day 168/Visit 6 to Visit 8).

- g If consent obtained.
- h After randomization. If, for any reason, the sample is not drawn pre-dose on Visit 3 (Day 1), it may be taken at any visit until the final follow-up visit/Early Discontinuation Visit.
- i Subjects collect 3 consecutive first morning void midstream urine samples (ideally day of visit and preceding 2 days [refrigerated overnight]) which are returned on the day of visit.
- j In the event that a dose cannot be administered within the window of the scheduled dosing date, the dose may be administered outside of the dosing window as long as it is at least 14 days prior to the next dose and recorded as a protocol deviation.
- k Subjects enrolled that have reached the Day 85 visit prior to Amendment 2 approval should continue in the study without the addition of dapagliflozin to their dosing regimen.

### 4.2.3 Follow-up Period

Table 7 shows all procedures to be conducted during the follow-up period.

Follow-up of subjects who discontinue MEDI3506 or dapagliflozin is detailed in Section 4.1.6.

Subjects who wish to withdraw from the study should be asked if they are willing to have an EOS visit prior to withdrawal.

**Table 7 Schedule of Follow-up Procedures**

Study Period	Follow-up Period
Visit Number	Visit 10/EOS
Procedure / Study Day	Day 230 (± 5 days)
Safety assessments:	
Physical examination (full) with weight	X
Vital signs	X
ECG	X
Assessment of AEs/SAEs	X
Concomitant medications	X
Blood collection for:	
Serum chemistry	X
CCI	X
CCI	X
Complete blood count with differential	X
PK (MEDI3506)	X
ADA (MEDI3506)	X
CCI	X
CCI	
Blood for future use a	X
Urine collection for:	
Urinalysis	X
UACR b	X
Pregnancy test (females of childbearing potential)	X
Exploratory biomarkers	X
Urine for future use a	X

ADA = anti-drug antibody(ies); AE(s) = adverse event(s); BNP = B-type natriuretic peptide;  
ECG = 12-lead electrocardiogram; EOS = end of study; CCI; PK = pharmacokinetics;  
SAE(s) = serious adverse event(s); CCI UACR = urine albumin:creatinine ratio.

NOTE: Investigator should ensure that all subjects are contacted by phone 1 day prior to every visit for assessing COVID-19 symptoms and signs and are asked to follow up suspected reports according to local guidelines.

a If consent obtained.

b Subjects collect 3 consecutive first morning void midstream urine samples (ideally day of visit and preceding 2 days [refrigerated overnight] which are returned on the day of visit.

## **4.3 Description of Study Procedures**

### **4.3.1 Efficacy**

The primary efficacy endpoint of change from baseline to Day 169 (Week 24) in UACR compared to placebo will be analyzed based on the Per Protocol Population. Urine will be collected for UACR analysis based on the schedule of study procedures in Table 5, Table 6, and Table 7. Containers for urine sample collection will be dispensed at Visit 1. Subjects will be reminded by phone call to bring in 3 first morning void midstream urine samples: day of visit and preceding 2 days (refrigerated overnight, which are return on the day of visit). Ideally, first morning void midstream urine samples should be collected after at least 6 hours of supine rest, even if the subject returns to sleep; if not possible/convenient, then first morning void midstream urine samples should be collected when the subject gets up for the day.

### **4.3.2 Medical History and Physical Examination, Electrocardiogram, Weight, Height, BMI Calculation, and Vital Signs**

In addition to the medical history, physical examinations, weight, height, body mass index (BMI) calculation, vital signs, and ECG assessments described below, additional assessments may be performed at the investigator's discretion.

#### **4.3.2.1 Medical History**

Complete medical history will include history of and current medical conditions, past or present cardiovascular disorders, respiratory, gastrointestinal, renal, hepatic, neurological, endocrine, lymphatic, hematologic, immunologic, psychiatric, genitourinary, menopausal status, drug and surgical history, or any other diseases or disorders. In relation to the study objectives, diagnosis date for T2DM and CKD will also be recorded.

#### **4.3.2.2 Physical Examination, Height, Weight, and BMI calculation**

Full and abbreviated physical examinations will be performed by a licensed healthcare provider (eg, physician, physician's assistant, or licensed nurse practitioner). Full physical examinations will include, but are not limited to, assessment of general appearance, head, ears, eyes, nose, throat, neck, skin, as well as cardiovascular, respiratory, abdominal, and nervous systems. Abbreviated physical examinations will include assessment of cardiovascular, respiratory, and nervous systems. Each clinically significant abnormal finding will be recorded in the medical history, and each treatment-emergent abnormality including injection-site reactions identified by assessing SC injection sites will be recorded as a TEAE. Physical examinations, weight, height, and BMI calculation will be performed according to the schedule of study procedures where indicated (Table 5, Table 6, and Table 7).

The focused cardiac exam conducted as part of the abbreviated physical examination will include:

- precordial palpation for LV displacement and parasternal lift, and
- auscultation for S3 gallop and increased intensity of P2.

Additional findings to document any volume overload/volume expansion will include:

- auscultation of lung fields for crackles, and
- assessment for jugular venous distension and lower extremity edema (if present at baseline, any changes to be noted at study visit).

Urogenital exam may be omitted at the discretion of the Principal Investigator.

Weight should be measured in light street clothes, without shoes, after a prior visit to the bathroom.

#### **4.3.2.3 Vital Signs**

BP will be measured at each study visit along with other vital signs of temperature, pulse, and respirations. The nominal timing of vital signs, ECGs, and blood draws is described (Section 4.2). Whenever vital signs, 12-lead ECGs, and blood draws are scheduled for the same nominal time, the blood draws should occur last.

For the first 2 doses of MEDI3506 or placebo, vital signs will be taken before and immediately after administration of investigational product, and at 30 minutes ( $\pm 5$  minutes) as well as 120 minutes ( $\pm 10$  minutes) thereafter or until stable, whichever is later. Following the observation period, subject discharge will be at the discretion of the investigator. For all other dosing visits, vital signs will be collected 30 minutes ( $\pm 5$  minutes) after administration of MEDI3506 or placebo or when stable.

The subject should be in a seated or supine position for at least 10 minutes prior to the collection of vital signs, as follows:

- Oral, axillary, or tympanic temperature
- Diastolic BP
- Systolic BP
- Heart (pulse) rate
- Respiratory rate

For each BP measurement, the same arm and the same appropriately sized BP cuff should be used.

Vital signs are to be recorded in the EDC system. Vital signs may be repeated once after an additional 5 minutes of rest. Clinically significant abnormalities in vital signs will be recorded as AEs.

#### **4.3.2.4 Assessment for Injection-site Reactions**

Site staff will check the injection site for local reactions and assess for any systemic reactions for 30 minutes post injection of MEDI3506 or placebo on designated visit days as described in Table 6. Local and systemic reactions will be recorded as AEs according to the criteria described in Section 5.1.

#### **4.3.2.5 Echocardiogram**

A transthoracic echocardiogram will be performed during screening to document baseline characteristics and screen for clinically significant congenital or valve disease or a reduction in LV ejection fraction of < 40% as described in Section 4.1.3. A subsequent transthoracic echocardiogram will be obtained at Visit 9 to reassess LV function and other cardiac parameters after treatment. Echocardiograms will be performed as described in a separate manual.

#### **4.3.2.6 Electrocardiogram**

At the visits specified in Table 5 and Table 7, 12-lead ECGs will be obtained after 10 minutes supine rest. Triplicate ECGs will be performed (all 3 ECGs within a 10-minute time period, at least 1 minute apart).

The investigator should date and sign the ECG tracing and record the clinical significance of any abnormal result on the tracing. The ECGs will be interpreted by a qualified physician (the investigator or qualified designee) at the clinical study site. The ECGs will be stored at the study site. ECG evaluation will be recorded in the electronic case report form (eCRF).

The same recorder should be used for each subject at each time point, if possible. Date and time settings should be checked at the start of each study day and aligned with an official timekeeper for all machines used in the study.

The investigator may add extra 12-lead ECG safety assessments if there are any abnormal findings or if the investigator considers it is required for any other safety reason.

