### STUDY ENDPOINTS

Primary endpoint:

- Change from baseline to Day 169 (Week 24) in urine albumin:creatinine ratio (UACR) compared to placebo

Secondary endpoints:

- Measures of safety and tolerability including but not limited to:
  - Incidence of treatment emergent adverse events (TEAEs) and treatment emergent serious adverse events (TESAEs)
  - Assessment of vital signs (systolic blood pressure [SBP], diastolic blood pressure [DBP], heart rate, respiratory rate and body temperature)
  - Electrocardiogram (ECG)

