### 2.2 Secondary Objectives and Associated Endpoints

**Table 2 Secondary Objectives and Associated Endpoints**

Type	Objective	Endpoint
Safety	To evaluate safety and tolerability of MEDI3506 with and without dapagliflozin in subjects with DKD	Measures of safety and tolerability including but not limited to: 
 
• Incidence of TEAEs and TESAEs
 
• Assessment of vital signs (SBP, DBP, heart rate, respiratory rate and body temperature)
 
• ECG
 
• LVEF as measured by echocardiogram
 

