#### **4.7.3 Considerations for SGLT2i and RAASi**

If a subject is on SGLT2i treatment prior to enrollment into this study, they must have been on a stable dose for at least 4 weeks prior to the randomization visit. Starting additional SGLT2i therapy during the study, before Day 169/Early Discontinuation Visit, is not permitted. Any existing SGLT2i treatment will be discontinued on Day 85. All subjects will receive 10 mg

dapagliflozin by mouth daily starting on Day 85 until Day 168. Starting additional SGLT2i therapy at or after Day 169/Early Discontinuation Visit is permitted.

In general, any dose changes of SGLT2i treatment should be avoided during the study unless due to medical necessity. If the subject needs to interrupt SGLT2i treatment for any reason, they should be allowed to re-start it again once the respective medical condition gets resolved.

Subjects who have started on the Phase 2a study prior to Amendment 2 will be transitioned to the Phase 2b and given 10 mg dapagliflozin starting on Day 85 (Week 12). Any existing SGLT2i treatment will be discontinued. Subjects who have completed 12 weeks of treatment prior to approval of Amendment 2 will continue on treatment with MEDI3506/placebo without dapagliflozin.

For patients with T2DM and albuminuria, clinical guidelines recommend treatment with ACEi or ARB and SGLT2i (dapagliflozin in this study) (de Boer et al, 2020). The recommendation of treating patients with T2DM, CKD, and an eGFR > 30 ml/min per 1.73 m^2 with an SGLT2i and RAASi is based on the highest level of evidence (1A) that these therapies are safe and efficient in reducing adverse kidney events.

Once daily 10 mg dapagliflozin has been studied in large cardiovascular and renal outcomes studies on top of standard of care, including ACEi or ARB (DAPA-HF and DAPA-CKD studies) (Heerspink et al, 2020b; McMurray et al, 2019). Among patients with CKD and T2DM, the risk of a composite of a sustained decline in eGFR of at least 50%, end-stage kidney disease, or death from renal or cardiovascular causes was significantly lower with dapagliflozin than with placebo. Hence, discontinuation of ACEi or ARB or dapagliflozin should be avoided. Permanent discontinuation should be regarded as a last resort.

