##### **4.8.4.3 Analysis of Vital Signs and ECGs**

Vital sign results and ECGs will be summarized using descriptive statistics at each time point by treatment group.

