  - 34 Table 5 (Schedule of Treatment Period Study Procedures): Footnote d, Clarified that transthoracic echocardiogram may be performed independently of other Visit 10 procedures within the visit window for additional flexibility.
  - 35 Table 5 (Schedule of Treatment Period Study Procedures): Footnote f, removed Day 169 PK sample collection as there will be no investigational product administered at this time point.
  - 36 Table 6 (Schedule of Follow-up Procedures): Height and BMI calculation were added for Visit 12 for an end of study visit assessment.
  - 37 Section 4.3.1 (Efficacy): Added clarification as to what constitutes a ‘first morning void’ sample.
  - 38 Section 4.3.2.2 (Physical Examination, Height, and Weight): Deleted “Weight assessment will be conducted at every study visit” to avoid redundancy with text in the same paragraph: “Physical examinations, weight, height, and BMI calculation will be performed according to the schedule of study procedures where indicated”
  - 39 Section 4.3.2.2 (Physical Examination, Height, and Weight): Specified that weight should be measured in light street clothes, without shoes, after a prior visit to the bathroom to ensure that measurements are under similar conditions.
  - 40 Section 4.3.2.2 (Physical Examination, Height, Weight, and BMI calculation): Added text for clarity and for consistency with Table 5 (Schedule of Treatment Period Study Procedures): 1) additional remote weight assessments will be obtained at least weekly at home using a remote digital scale for the first 12 weeks after initial dose of investigational product; 2) subjects will be trained on how to use the app and weight scale by investigators or designee and take the scale home at Visit 3; and 3) if needed, subjects may be provided with a smartphone in order to use the app, and that data will be available to site and sponsor in real time for review.
  - 41 Section 4.3.2.3 (Vital Signs): Revised the order of procedures for vital signs to occur prior to 12-lead ECG for consistency with the Schedule of Study Procedures.
  - 42 Section 4.3.2.6 (Electrocardiogram): Revised text to state that only ECG evaluation will be recorded in the eCRF and removed the specific ECG variables (RR, PR, QRS, QT intervals).

- 43 Section 4.3.3 (Clinical Laboratory Tests): Clarified that clinical laboratory safety tests including serum pregnancy tests will be performed in a licensed local or licensed central clinical laboratory to avoid ambiguity.

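### ECG is a secondary safety endpoint, but the only scheduled post-baseline ECG comes about 89 days after the last MEDI3506 dose, so it cannot describe ECG findings during treatment

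*Protocol*

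**What the plan says.** The synopsis and Table 2 both list ECG as a secondary safety endpoint. The objective it serves in Table 2 is "To evaluate safety and tolerability of MEDI3506 with and without dapagliflozin in subjects with DKD".

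Section 4.3.2.6 sets the timing: "At the visits specified in Table 5 and Table 7, 12-lead ECGs will be obtained after 10 minutes supine rest". Table 5 marks the ECG at screening Visit 1, within Day −37 to Day −3. Table 7 marks it at Visit 10/EOS, Day 230 (± 5 days). The ECGs are triplicate, and the eCRF holds the physician's evaluation of them.

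Table 6 covers Visits 3 to 9 (Day 1 to Day 169) and the Early Discontinuation Visit. Its safety block starts with "Physical examination (abbreviated) with weight" and continues with vital signs, echocardiogram, adverse events and concomitant medications. It has no ECG row.

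The planned analysis in Section 4.8.4.3 is: "Vital sign results and ECGs will be summarized using descriptive statistics at each time point by treatment group".

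**The concern.** An endpoint meant to inform on safety with and without dapagliflozin needs at least one planned reading while subjects are being treated. Here the two planned readings lie before the first dose and two to three months after dosing ends. An ECG change that appears during treatment and then reverses would be missed in every arm. The arms could look alike at Day 230 whether or not they had differed during treatment.

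This is not a detail that the SAP can settle. If the protocol is followed exactly, the treatment-period data do not exist for any of the roughly 565 subjects planned, apart from ECGs that an investigator chooses to add.

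**Working it through.** The protocol states no interval from last dose to ECG, so there is no figure of its own to reproduce. The check is day arithmetic on the visit schedule.

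**Inputs**
- MEDI3506/placebo dosing: the Table 6 row "IP administration (MEDI3506/placebo") carries six marks, read as Visits 3 to 8, which are Days 1, 29, 57, 85, 113 and 141. The gaps are all 28 days, and Visit 9 has no mark. The amendment log agrees for Day 169: "there will be no investigational product administered at this time point". It is used only as corroboration.
- Dapagliflozin: Section 4.7.3 says "All subjects will receive 10 mg" daily from Day 85, ending on Day 168.
- Post-baseline ECG: Day 230 ± 5 (Table 7).
- EOS after early discontinuation of MEDI3506: 60 ± 5 days after the last visit performed (Section 4.1.6).

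**Results**
- Last MEDI3506 dose to ECG: 230 − 141 = 89 days. With both ± 5-day windows, the shortest is 225 − 146 = 79 and the longest is 235 − 136 = 99.
- Last dapagliflozin day to ECG: 230 − 168 = 62 days.
- Early discontinuation, assuming the Early Discontinuation Visit falls about 28 days after the last dose: 28 + 60 = 88 days. Allowing ± 10 on the 28 days and ± 5 on the 60 days gives 73 to 103.
- Scheduled ECGs from Day 1 to Day 169: none.

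**If the ECG were taken at Day 169 instead**
- 169 − 141 = 28 days after the last MEDI3506 dose, which is one dosing interval.
- 169 − 168 = 1 day after the last dapagliflozin day.

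**Is the missing row real?** The redacted rows of Table 6 lie in its blood and urine blocks, while the safety block is readable. Section 4.3.2.6 independently names Tables 5 and 7 and leaves out Table 6. Section 4.2 gives an order for vital signs, ECGs and blood draws that coincide, but that rule schedules no ECG.

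**A related mismatch.** Section 3.1.1 gives a follow-up of 70 days, which would put EOS at 168 + 70 = Day 238. Table 7 says Day 230. On the 70-day reading the ECG would come 238 − 141 = 97 days after the last dose. The two places should be reconciled, but the conclusion is the same on either.

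**The case against.** The strongest reply is that Sections 4.3.2.6 and 4.8.4.3 and Tables 5 to 7 agree with one another. On this view the timing is a design choice. ECG is one item in an open-ended safety list, it is summarized only descriptively, and no hypothesis rests on it. That is fair and limits the weight of the point. It does not remove the mismatch between the objective and the time of measurement.

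Three stronger readings are tempting, and the protocol does not support them.

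- A reader might infer that cardiac safety goes unwatched during treatment. It does not. A cardiac-focused examination and vital signs are done at every treatment visit and at the Early Discontinuation Visit. An echocardiogram is done at Visit 9 and at the Early Discontinuation Visit. LVEF and BNP are separate safety endpoints. Heart failure is an adverse event of special interest, and the DSMB reviews data by treatment group.
- A reader might infer that the ECG result would be presented as a clean bill of health. No section says so.
- A reader might infer the same gap for urinalysis, which Table 6 appears to mark only at Day 1. The urine rows in the available text are misaligned, and the footnote attached to the urinalysis row is missing, so this cannot be established.

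Investigators may add ECGs under Section 4.3.2.6. Because an abnormality or a safety concern triggers them, they are selective and cannot stand in for a planned reading by arm.

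**Conclusion.** The point holds as a mismatch between an endpoint and its sampling time. No scheduled ECG falls between Day 1 and Day 169. The single post-baseline ECG comes about 89 days (79 to 99) after the last MEDI3506 dose and about 62 days after the last dapagliflozin day. The planned summary can show a persistent or late ECG change by arm, but not findings during treatment, with or without dapagliflozin. It is worth correcting, but it touches neither the primary endpoint nor the on-treatment monitoring for heart failure.

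This rests on reading the six dosing marks as Days 1 to 141 and on subjects completing treatment to schedule. Day 230 is after the end of dosing. A reader might go further and call it free of MEDI3506, but the available text gives no half-life and MEDI3506 concentrations are still sampled at Visit 10, so residual exposure cannot be judged.

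**What to change.** Reconcile the endpoint with its sampling time in one of two ways.

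1. Take the existing EOS triplicate ECG at Visit 9 (Day 169) and at the Early Discontinuation Visit instead, alongside the echocardiogram already scheduled there. Update Tables 6 and 7 and Section 4.3.2.6. For completers this adds no procedure. Describe the endpoint as the ECG evaluation at the end of the dapagliflozin period compared with screening. A single Day 169 reading says nothing about Days 1 to 84, before study dapagliflozin starts, so the endpoint should not claim to cover both parts of the objective. The costs are an amendment to the schedule tables and the loss of the Day 230 follow-up ECG.
2. Keep the schedule, and describe ECG in Table 2 and Section 4.8.4.3 as a post-treatment follow-up assessment and not as evidence of on-treatment safety. This costs only wording, but it gives up any planned on-treatment ECG data.

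The first is preferable, because it yields a planned ECG close to treatment at visits that subjects already attend.
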